**Suppression of Phoenixin-14 Predicts Mortality in Sepsis: Evidence from
Serum Levels and Gene Expression**

[name] [name]

30.04.2025

Department of Anesthesiology and Reanimation, Firat University Medicine Faculty Hospital,
Elazig 23300, Turkey

Study Protocol

Study Design and Patients

In this prospective observational cohort study, patients aged 18 years and older admitted to our tertiary intensive care unit with diagnoses of sepsis and/or septic shock were evaluated. Ethical approval was obtained from the Firat University Non-Interventional Research Ethics Committee on March 27, 2024, with the number 23376. The entire study was funded by the Firat University Scientific Research Projects Coordination Unit (FUBAP), under project number TF.24.11. Our study adhered to the Helsinki Declaration and the Strengthening the Reporting of Observational Studies in Epidemiology (STROBE) guidelines.

The treatment protocol for patients was followed according to the Sepsis-3 guidelines (1), and antibiotic therapy was administered in consultation with an infectious disease specialist, aiming at the source of sepsis. Septic shock was also defined according to the Sepsis-3 guidelines (1), based on the requirement for vasopressor support to maintain adequate mean arterial pressure despite adequate fluid resuscitation.

Patients under the age of 18, patients who were discharged/transferred or died within 72 hours after being diagnosed with sepsis, patients/relatives who refused to participate in the study, pregnant women, patients using chronic steroids, patients whose blood samples were collected

under inappropriate conditions, and patients with a history of malignancy or immunosuppression were also excluded from the study.

The study was started with participants who agreed after signing an informed consent form.

Collection of Blood Samples and Data

At the time of ICU admission, parameters such as age, gender, body mass index (BMI), comorbidities, infection focus, complete blood count, CRP, procalcitonin, Acute Physiology and Chronic Health Evaluation (APACHE) II score, Sequential Organ Failure Assessment (SOFA) score, vasopressor requirement, mechanical ventilation need, and renal replacement therapy requirement were recorded. On the first day of hospitalization, 3 mL of blood was routinely collected from patients for biochemical analysis. The levels of IL-6, TNF- α , IL-1 β , IL-10, and PNX14 were measured using real-time PCR, while serum levels were determined using ELISA. Blood samples were collected once at ICU admission to assess baseline PNX-14 levels for early prognostic evaluation.

RNA Isolation

Total RNA was isolated from peripheral blood samples using the NucleoSpin RNA Blood kit (Macherey-Nagel, Germany) according to the manufacturer's instructions. RNA concentration and purity were assessed using a Qubit 2.0 Fluorometer (Thermo Fisher Scientific).

RNA Quality Control – Agarose Gel Electrophoresis

RNA integrity was assessed by agarose gel electrophoresis. Briefly, RNA samples were separated on a 1% agarose gel and visualized using a gel documentation system to confirm RNA integrity, according to standard laboratory procedures.

RNA Concentration Measurement – Qubit Fluorometric Method

RNA concentration and quality were assessed using a Qubit 2.0 Fluorometer (Thermo Fisher Scientific, USA) and the Qubit RNA HS Assay Kit, following the manufacturer's recommended protocol.

cDNA Synthesis

Complementary DNA (cDNA) was synthesized from total RNA using the High-Capacity cDNA Reverse Transcription Kit (Thermo Fisher Scientific, USA) as per the manufacturer's protocol.

Quantitative Real-Time PCR (qRT-PCR)

Quantitative real-time PCR analysis was performed using SYBR Green Master Mix (AMPLIFYME SYBR Universal Mix) on an Applied Biosystems StepOnePlus system. GAPDH was used as the reference gene due to its reported expression stability in peripheral blood samples under inflammatory conditions. Relative gene expression was calculated using the $2^{-\Delta\Delta Ct}$ method, with GAPDH as the internal control. In the absence of a healthy control group, the survivor group was used as the calibrator for relative expression analysis. Primer sequences are listed in Table 1.

Table 1. Primers used in the study

	Forward Primer	Reverse Primer
GAPDH	5'-GAA GGT GAA GGT CGG AGT C-3'	5'-GAA GAT GGT GAT GGG ATT TC-3'
PNX-14	5'-CGG CTT CAT CTC CCT GAT CG -3'	5'ACA GCC CTC TCA TTT CCT GC-3'

GAPDH (glyceraldehyde-3-phosphate dehydrogenase; PNX-14: Phoenixin14

ELISA Protocol

Serum levels of Phoenixin-14 and cytokines were measured using commercially available ELISA kits (BT Lab, Shanghai, China) according to the manufacturer's instructions.

End points

Primary endpoint: the relationship between PNX14 levels and in-hospital mortality in patients with sepsis or septic shock. Secondary endpoints: to evaluate the tendency of PNX-14 levels to be suppressed at the molecular level in patients with sepsis and their potential as a translational biomarker. Additionally, to assess the relationship between PNX14 and SOFA scores, APACHE II scores, septic shock, requirements for mechanical ventilation or renal replacement therapy, and ICU length of stay in patients with sepsis. The correlation between PNX14 levels and those of CRP, procalcitonin, IL-1 β , IL-6, IL-10, and TNF- α was also examined as part of the endpoints.

Statistical Analysis

Before the study, calculations were conducted using G*Power 3.1 with 80% power, $\alpha = 0.05$, and an expected medium effect size ($d = 0.5$), indicating that at least 64 patients were needed. This requirement was met by including 77 patients in the study.

The data were analyzed using IBM SPSS Statistics for macOS, version 29.0 (IBM Corp., Armonk, NY, USA). Descriptive statistics for continuous variables are presented as mean \pm standard deviation for normally distributed data and median (Q1–Q3) for non-normal data; categorical variables are shown as frequency (percentage). Group comparisons between developing and non-developing patients were conducted with the independent samples t-test for normally distributed continuous data and the Mann–Whitney U test for non-normal data. Normality of continuous variables was checked with the Kolmogorov–Smirnov test. For categorical variables, either the Pearson chi-square test or Fisher's exact test was used, as appropriate.

The relative quantification (RQ, $2^{-\Delta\Delta Ct}$) values from qPCR experiments were compared between two groups (Dead and Survived). The distribution of both groups was assessed using the Shapiro–Wilk test prior to analysis, and the assumption of normality was not rejected (D group $p=0.12$; S group $p=0.17$). Homogeneity of variances was evaluated with the Levene test, which indicated unequal variances ($p=0.018$). Therefore, the differences between groups were analyzed using the Welch independent samples t-test. Additionally, the nonparametric Mann–Whitney U test was performed to verify robustness.

The ability of each biomarker to predict mortality was evaluated using ROC (receiver operating characteristic) curve analysis. The area under the curve (AUC), 95% confidence interval, optimal cut-off value, sensitivity, specificity, Youden index, and p-values were calculated. Since PNX-14 levels were inversely related to mortality in the ROC analysis, the analysis was performed with the reversed direction. Comparison of ROC curves for PNX-14 versus procalcitonin and CRP was conducted using the DeLong test.

To identify variables linked to mortality, univariate logistic regression analysis was conducted. Variables that proved significant were included in the multivariate logistic regression model to determine independent risk factors. The Backward-Wald method was employed for variable selection. Multicollinearity among independent variables was evaluated using the variance inflation factor (VIF) and tolerance values; VIF less than 5 and tolerance values between 0.40 and 0.80 were considered acceptable. The relationships between PNX, inflammatory biomarkers, and clinical severity scores were analyzed using Pearson or Spearman correlation tests, depending on the distribution of the variables, with correlation coefficients (r) and p-values reported. In all analyses, a p-value less than 0.05 was regarded as statistically significant.

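### The 72-hour exclusion is not carried into the endpoint or the prediction claims, which therefore describe later death among patients still present at about 72 hours

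*Combined protocol and SAP*

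**What the plan says.** The Study Design and Patients section describes the cohort broadly: "patients aged 18 years and older admitted to our tertiary intensive care unit with diagnoses of sepsis and/or septic shock were evaluated". Its exclusion list then removes "patients who were discharged/transferred or died within 72 hours after being diagnosed with sepsis". The clock runs from diagnosis, and the text does not say whether discharge or transfer means leaving the ICU or leaving the hospital.

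Collection of Blood Samples and Data fixes the time and purpose of the measurement: "Blood samples were collected once at ICU admission to assess baseline PNX-14 levels for early prognostic evaluation".

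End points gives "Primary endpoint: the relationship between PNX14 levels and in-hospital mortality in patients with sepsis or septic shock". Statistical Analysis says "The ability of each biomarker to predict mortality was evaluated using ROC (receiver operating characteristic) curve analysis", lists the AUC, cut-off, sensitivity and specificity to be reported, and adds logistic regression on mortality. The title reads "Suppression of Phoenixin-14 Predicts Mortality in Sepsis".

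The exclusion list is the only place where 72 hours appears. The analysed number is given ("This requirement was met by including 77 patients in the study"), but not the number removed under this rule.

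**The concern.** Most of the exclusions (age, pregnancy, chronic steroid use, malignancy, immunosuppression) can be checked when the blood is drawn. Survival and continued presence to 72 hours normally cannot. A death at 48 hours is an in-hospital sepsis death, so it is a primary-endpoint event, yet the rule drops it. Patients who leave early are dropped too, and they are probably among the milder cases.

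The analysis is therefore a landmark analysis at about 72 hours that is not labelled as one. A clinician with an admission result does not know whether the patient will belong to the analysed group. The reported cut-off and its sensitivity and specificity may not hold for all the patients in whom the test would be used. Without counts by reason, the reader cannot judge how far the two groups differ.

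**Working it through.** **1. The text side by side.**

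| Element | Stated | 72-hour condition? |
|---|---|---|
| Exclusion | Death, discharge or transfer within 72 h of diagnosis | Yes |
| Sample | Once, at ICU admission | No |
| Primary endpoint | In-hospital mortality in sepsis or septic shock | No |
| ROC and regression | Mortality | No |
| Title | Mortality in sepsis | No |

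Diagnosis time and sampling time are not linked. For a patient diagnosed well before ICU admission, part or all of the window may have passed by sampling. Hence *normally* after the sample, and *about* 72 hours.

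**2. What the documents allow to be computed.** They give no mortality rate, no count of early deaths or departures and no AUC, so there is no plan figure to reproduce. Only d = 0.5 and n = 77 (Statistical Analysis) are taken from the documents below. Everything else is assumed.

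**3. Simple bound using d = 0.5.** Suppose later deaths differ from survivors by d = 0.5 (normal, equal variance), and early leavers have the same PNX-14 distribution as other survivors. The retained AUC is Φ(0.5/√2) = 0.638. If a share e of deaths is early, with difference x, the AUC in all sampled patients is (1 − e) × 0.638 + e × Φ(x/√2). With e = 0.4:
- x = 0: 0.6 × 0.638 + 0.4 × 0.500 = 0.583
- x = 0.5: 0.638
- x = 1.5: 0.6 × 0.638 + 0.4 × 0.856 = 0.725

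The retained figure can be too high, correct or too low.

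**4. Competing-hazards simulation** (1,000,000 patients per row). The marker is sign-reversed PNX-14, standard normal. The death hazard is 0.035·exp(bx) per day and the live-departure hazard 0.05 per day, independent of x. The clock starts at sampling, and exits before day 3 are dropped. If a share q leaves before day 3, the number removed per 77 kept is 77q/(1 − q).

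Hand check with b = 0 to day 3: q = 1 − exp(−3 × 0.085) = 0.225. Removed: 77 × 0.225/0.775 = 22. Deaths among them: 22 × 0.035/0.085 = 9.

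| b per SD; early death hazard if changed | AUC, all → retained | OR per SD | Removed (deaths) per 77 kept | Shift/SE |
|---|---|---|---|---|
| 0.5 | 0.634 → 0.632 | 1.64 → 1.64 | 24 (10) | 0.03 |
| 0.6 | 0.658 → 0.656 | 1.82 → 1.82 | 24 (11) | 0.04 |
| 0.9 | 0.721 → 0.714 | 2.46 → 2.46 | 26 (13) | 0.13 |
| 0.6; 0.07/day | 0.669 → 0.652 | 1.91 → 1.81 | 37 (23) | 0.27 |
| 0 then 0.6 | 0.623 → 0.659 | 1.57 → 1.83 | 22 (9) | 0.55, upward |
| 0.6; 0.15/day | 0.688 → 0.648 | 2.08 → 1.82 | 69 (53) | 0.60 |
| 0.9 then 0.3 | 0.625 → 0.579 | 1.60 → 1.35 | 26 (13) | 0.68 |
| 0.9 then 0.3; 0.07/day | 0.657 → 0.577 | 1.82 → 1.35 | 40 (26) | 1.19 |

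SE is the Hanley–McNeil standard error at the retained AUC and mortality with n = 77, and runs from 0.062 to 0.067. Example, 0.9 then 0.3: retained mortality is 40.4%, so about 31.1 deaths and 45.9 survivors. With A = 0.579, A/(2 − A) = 0.407 and 2A²/(1 + A) = 0.425. The variance is [0.244 + 30.1 × 0.072 + 44.9 × 0.089]/(31.1 × 45.9) ≈ 0.0045, so SE = 0.067. The shift of 0.046 is about 0.7 SE.

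The unchanged odds ratio in the first three rows is built into the model: with constant competing hazards, logit P(death | x) = ln(0.035/0.05) + bx, whatever the starting day.

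**5. If leaving the ICU is what counts.** With b = 0.6, base hazards and 5 to 15% ward death at the mean marker level, about 24 are removed per 77 kept. Of these, 11 are ICU deaths and 13 live departures, of whom 0.8 to 2.1 later die in hospital. The AUC shift is 0.003 to 0.004. On this reading the site can still observe the outcomes of the ward patients it drops, and ICU length of stay, a secondary endpoint, loses its short end. If transfer to another hospital is meant, the outcome may be unknown.

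**The case against.** The rule is disclosed in the usual place. Eligibility criteria define the population for everything that follows, and the title and endpoint do not repeat the other exclusions either. No single sentence claims prediction of in-hospital mortality from an admission sample in all sepsis patients; that reading combines the title, endpoint, sampling text and ROC text. No numerical harm is shown: the base case moves the AUC by at most 0.13 SE, and larger shifts need an effect that switches at day 3, a raised early death hazard, or both. Counts by reason belong in a results report.

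Much of this stands. The simulation neither establishes nor excludes bias, so the point cannot rest on it. The counts and the definition of departure would, on their own, be missing detail. What fails is the analogy with the other exclusions. Those can be applied at admission, whereas this one conditions on the future and removes outcome events. Disclosure in the list does not make an endpoint and title without that condition accurate. The combined reading is also fair, because none of the four places carries the limit.

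**Conclusion.** The concern holds and should be fixed. As written, the plan yields estimates for death after about 72 hours among patients still present then, while the endpoint, the prediction analyses and the title carry no such limit. The analysis is not invalid for the narrower question.

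The size and direction of any numerical bias are unknown. In the assumed scenarios the AUC shift runs from negligible (0.03 SE) to 1.19 SE downward, and 0.55 SE upward in one case. These figures depend wholly on assumed hazards and on a clock starting at sampling. The conclusion depends on neither; it follows from the wording and from the usual order of sampling and exclusion.

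**What to change.** In this order:

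1. State whether discharge or transfer means from the ICU or from the hospital, and whether the 72 hours run from diagnosis or from sampling.
2. Restate the primary endpoint and every ROC and regression claim as in-hospital death after 72 hours among patients alive and still in the ICU (or hospital, according to step 1) at 72 hours. Qualify the title and the early-prognosis wording to match.
3. Report the numbers removed separately for death, discharge and transfer.

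Where consented, stored admission samples and outcomes of excluded patients exist, add a labelled sensitivity analysis of all sampled patients. Count early in-hospital deaths as events and early live hospital discharges as non-events, and give best-case and worst-case bounds for transfers with unknown outcome.

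Do not change the primary population now. The direction of the result is already known ("Since PNX-14 levels were inversely related to mortality in the ROC analysis, the analysis was performed with the reversed direction"), so a switch would be data-driven.

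The cost is some rewording, one clarifying sentence, three counts in the flow diagram and a narrower stated population. The sensitivity analysis needs extra assays and outcomes and may be impossible, since the documents do not say that excluded patients consented or that their samples were kept.

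### The qPCR comparison of PNX-14 by outcome rests on one reference gene not checked against outcome and on unsorted blood, so a GAPDH or white-cell difference could create or mask apparent suppression

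*Combined protocol and SAP*

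**What the plan says.** All of this is in the combined protocol and SAP.

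- **RNA source** (RNA Isolation): "Total RNA was isolated from peripheral blood samples using the NucleoSpin RNA Blood kit". No sorting or enrichment of cell types is described.
- **Reference gene** (Quantitative Real-Time PCR): "GAPDH was used as the reference gene due to its reported expression stability in peripheral blood samples under inflammatory conditions". Table 1 lists primers for GAPDH and PNX-14 and for no second reference gene. No check of GAPDH in this cohort is described.
- **Calibrator** (same section): "In the absence of a healthy control group, the survivor group was used as the calibrator for relative expression analysis".
- **Comparison** (Statistical Analysis): "The relative quantification (RQ, $2^{-\Delta\Delta Ct}$) values from qPCR experiments were compared between two groups (Dead and Survived"). The tests are Welch's t-test, with Mann–Whitney as a robustness check. Both are unadjusted.
- **Blood count** (Collection of Blood Samples and Data): the admission record covers "comorbidities, infection focus, complete blood count, CRP, procalcitonin". The text does not say whether the count includes a differential, and no stated analysis uses it in the expression comparison.

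**The concern.** The readout is PNX-14 signal relative to GAPDH signal, averaged over whatever cells are in the sample. A lower ratio in non-survivors has at least three explanations: less PNX-14 transcript per cell, more GAPDH, or fewer of the cells that carry the transcript. The stated reason for choosing GAPDH does not separate them. Every patient here is septic, so stability under inflammation leaves open whether GAPDH differs between septic patients who die and those who live.

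No planned step removes the ambiguity:

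- The survivor calibrator is one constant applied to every patient, so it cancels from the comparison and cannot absorb a group difference in GAPDH.
- Mann–Whitney uses the same GAPDH-normalised values as Welch.
- The gel and Qubit steps address RNA integrity and amount.
- The logistic model has mortality as its response, and blood-count terms enter only if they pass univariate screening and survive backward selection.

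At stake is the interpretation of the gene-expression evidence. The title puts suppression forward as a predictor of death and names gene expression as one of two lines of evidence. A secondary endpoint concerns suppression at the molecular level in sepsis. The qPCR result is the only transcript-level evidence for either.

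**Working it through.** The documents give no figure for GAPDH stability or cell mix, so there is nothing to reproduce. The size of the effect follows from the RQ formula. The inputs below are assumptions unless marked otherwise.

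**1. Shift in GAPDH**

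ΔCt = Ct(PNX-14) − Ct(GAPDH), and RQ = 2^−(ΔCt − mean survivor ΔCt). If GAPDH Ct is s cycles lower in non-survivors and PNX-14 Ct is unchanged, their ΔCt rises by s and their RQ is multiplied by 2^−s.

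| GAPDH Ct in non-survivors | Spurious RQ ratio |
|---|---|
| 1 cycle lower | 2^−1 = 0.50 |
| 0.5 lower | 2^−0.5 = 0.71 |
| 0.25 lower | 2^−0.25 = 0.84 |
| 0.5 higher | 2^0.5 = 1.41 |

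The last row shows masking: a true ratio of 0.71 combined with a GAPDH Ct 0.5 higher would be seen as 0.71 × 1.41 = 1.00.

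**2. Shift in cell mix**

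Assume lymphocyte shares of 20% in survivors and 8% in non-survivors, equal GAPDH per cell, and no change in expression within any cell type. Let lymphocytes carry r times the transcript of other cells. The RQ ratio is then (0.08r + 0.92) / (0.20r + 0.80).

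| r | RQ ratio |
|---|---|
| 0 | 0.92/0.80 = 1.15 |
| 0.25 | 0.94/0.85 = 1.11 |
| 4 | 1.24/1.60 = 0.78 |
| 10 | 1.72/2.80 = 0.61 |

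The direction depends on which cells carry the transcript, and the documents do not say.

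**3. Effect on the planned tests**

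A simulation used 77 patients (the number included, from Statistical Analysis), no true PNX-14 difference, 10,000 runs, ΔCt SD of 1.0 or 1.5, and a dead/survived split of 38/39 or 26/51. SDs and splits are assumptions; the documents do not give the numbers dead and survived. Only the downward direction was simulated.

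| GAPDH Ct lower by | Welch on RQ, p < 0.05 | Mann–Whitney, p < 0.05 |
|---|---|---|
| 0 | 4.2–5.1% | 4.3–5.0% |
| 0.5 | 20–51% | 26–56% |
| 1.0 | 62–97% | 76–99% |

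With no shift, both tests hold close to 5%. With a shift, Mann–Whitney gives no protection.

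**4. What a GAPDH check could show with 77 patients**

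At a 38/39 split and an assumed GAPDH Ct SD of 1.0, the standard error of the difference is √(1/38 + 1/39) = 0.228. The 95% half-width is about 1.99 × 0.228 = 0.45 cycle. An observed difference of exactly zero would still allow ratios from 2^−0.45 = 0.73 to 2^0.45 = 1.37. A non-significant GAPDH difference would therefore not establish stability.

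**The case against.** The strongest reply is that this is a possibility and not a finding. The plan gives a reason for GAPDH. Nothing in the documents shows that GAPDH differs by outcome, which cells carry PNX-14, or how cell shares differ between the groups. That stands.

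A reader might go further and infer that the reported suppression is an artefact, or that the link with mortality falls. The documents support neither. The bias can run in either direction, and serum PNX-14 is measured by ELISA, which does not involve GAPDH or blood-cell RNA. Nor does the secondary endpoint in End points tie suppressed gene expression to death: it speaks of suppression in patients with sepsis, while mortality belongs to the primary endpoint.

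A second reply is that the stated purpose of the admission sample is early prognosis. A whole-blood transcript can predict death whatever cell shift lies behind it, so the unadjusted comparison is legitimate for that purpose. This also stands. Adjustment answers a different question, about expression for a given cell mix, and it matters only when the result is read as suppressed transcription.

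A third reply concerns feasibility. A differential count is not mentioned, and equal RNA input to cDNA synthesis is not stated. Without equal or known input, raw GAPDH Ct also reflects the amount of RNA loaded. The remedy must therefore be conditional.

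None of these replies supplies the missing check on GAPDH by outcome or allows the competing explanations to be told apart.

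**Conclusion.** The point holds as a limit on what the qPCR comparison can show. With one reference gene unchecked against outcome, unsorted RNA and no account of cell mix, the plan cannot separate a change in PNX-14 transcription from a change in GAPDH or in white-cell composition. Half a cycle of GAPDH in either direction gives a ratio of 0.71 or 1.41. The cell-mix illustration runs from 1.15 to 0.61.

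These sizes rest on assumed Ct shifts, lymphocyte shares, expression ratios and equal GAPDH per cell. The simulated rejection rates also rest on assumed SDs and group splits. They show what is possible, not what happened. The serum evidence and the prognostic use of an unadjusted whole-blood measure are unaffected. The correction is worth making because it bears on whether suppressed gene expression can be concluded, and the first step uses values that must already exist, since RQ cannot be computed without them.

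**What to change.** 1. Report the dead-minus-survived difference in GAPDH Ct with its 95% CI, at equal RNA input or adjusted for the measured RNA input. Convert the limits to ratios and read the RQ difference against their size. Do not use a significance test as a pass or fail rule.
2. If the recorded blood count includes a differential, add a sensitivity regression of ΔCt on outcome with admission neutrophil and lymphocyte counts as covariates. Report the adjusted estimate and its CI beside the unadjusted one, which remains valid for prognosis. Loss of significance after adjustment should not by itself be read as proof of a cell-mix effect.
3. If these checks cannot be done, or do not support stability, say so. Describe any reduction as lower GAPDH-normalised whole-blood PNX-14 transcript that may reflect GAPDH or cell mix, and not as suppressed transcription.

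**Cost.** No new assay is needed, provided that RNA input is known and a differential was recorded. If either is missing, the cost is a change of wording. The two covariates widen the interval, possibly more than slightly if cell counts track death closely.

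### The secondary endpoint on PNX-14 being suppressed in sepsis cannot be answered as worded, because the study has no non-septic reference; the only molecular contrast it delivers is deaths against survivors.

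*Combined protocol and SAP*

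**What the plan says.** All references are to the combined protocol and SAP.

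- **End points.** The first secondary endpoint is "to evaluate the tendency of PNX-14 levels to be suppressed at the molecular level in patients with sepsis", followed by "and their potential as a translational biomarker". No reference group, reference value or earlier time point is named. The primary endpoint is "the relationship between PNX14 levels and in-hospital mortality in patients with sepsis or septic shock", with no assay named.
- **Study Design and Patients.** Those evaluated were adults "admitted to our tertiary intensive care unit with diagnoses of sepsis and/or septic shock were evaluated".
- **Collection of Blood Samples and Data.** "Blood samples were collected once at ICU admission to assess baseline PNX-14 levels for early prognostic evaluation". On assays, the section says that the cytokines and "PNX14 were measured using real-time PCR, while serum levels were determined using ELISA".
- **Quantitative Real-Time PCR (qRT-PCR).** "In the absence of a healthy control group, the survivor group was used as the calibrator for relative expression analysis".
- **Statistical Analysis.** The one group comparison described for the qPCR values is RQ in the Dead group against RQ in the Survived group, by Welch t-test with a Mann–Whitney check. The sample is 77 patients.
- **Title.** "Suppression of Phoenixin-14 Predicts Mortality in Sepsis", with serum and gene expression listed as two sources of evidence.

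**The concern.** *Suppressed* is a comparative word. Applied to patients with sepsis, it most naturally means lower than it would be without sepsis. The plan has no data on that state.

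What is at stake is the conclusion the study may draw. As worded, the endpoint would let a lower RQ in those who died be reported as evidence that sepsis suppresses PNX-14. The same data would arise if sepsis raised PNX-14 in every patient, but less in those who died. The qRT-PCR section discloses that there is no healthy control, but the endpoint is not narrowed to match.

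**Working it through.** The plan gives no figure to reproduce here. The check is whether any planned analysis could respond to an effect of sepsis common to all patients.

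**1. Inputs.** All patients septic (Study Design and Patients); one sample each (Collection of Blood Samples and Data); survivors as calibrator (qRT-PCR section); Dead against Survived as the qPCR comparison (Statistical Analysis). Assumption: the calibrator is the survivors' mean dCt, m_S; the plan does not say which summary was used.

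**2. qPCR.** For patient i, RQ_i = 2^-(dCt_i - m_S). Suppose sepsis shifts every patient's dCt by c cycles. Then

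(dCt_i + c) - (m_S + c) = dCt_i - m_S.

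Every RQ_i is unchanged for any c, positive or negative, and so is every test on RQ. In survivors the mean of log2 RQ is -(m_S - m_S) = 0, so their geometric mean RQ is 2^0 = 1 by construction, whatever sepsis did. With the survivors' median as calibrator the cancellation still holds, but the geometric mean need not be exactly 1.

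**3. Illustration with assumed values (not study data).** Let mean dCt be 8 in survivors and 9 in deaths. The deaths' geometric mean RQ is 2^-(9 - 8) = 0.5. Now add a non-septic mean dCt, which the study does not observe:

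| Assumed non-septic dCt | Survivors vs non-septic | Deaths vs non-septic | Deaths vs survivors |
|---|---|---|---|
| 6 | 2^-(8 - 6) = 0.25 | 2^-(9 - 6) = 0.125 | 0.5 |
| 10 | 2^-(8 - 10) = 4 | 2^-(9 - 10) = 2 | 0.5 |

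In the first row sepsis lowers expression in everyone; in the second it raises it in everyone. The study sees only the last column, which is the same in both. A simulation with 40 survivors and 37 deaths around these means (SD 1, also assumed) agreed: adding 0, 1 or 3 cycles to every patient gave geometric mean RQ of 1.000 in survivors and 0.538 in deaths each time.

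**4. Serum.** Suppose sepsis multiplies every patient's serum value by k > 0.

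- The mean difference and its standard error both scale by k, so the t and Welch t statistics are unchanged.
- Ranks are unchanged, so Mann–Whitney U, AUC, the DeLong comparison and Spearman correlation are unchanged. Pearson r is unchanged too.
- The logistic coefficient and its standard error both scale by 1/k, so the Wald z is unchanged.

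Group means and the ROC cut-off do move with k, but the documents give no non-septic value to set them against. So k cannot be identified either.

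**5. What remains.** Neither c nor k can be recovered. For the molecular data, the contrast delivered is deaths against survivors, within sepsis.

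**The case against.** The strongest reply is that the comparator is missing from one sentence, not from the plan. The qRT-PCR section names survivors as calibrator, the Statistical Analysis compares Dead with Survived, and the title uses suppression as a predictor of death within sepsis. On that view the only reading the plan implements is lower PNX-14 in those who die, which is answerable. No section concludes that sepsis lowers PNX-14, and the missing control is openly disclosed.

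Much of this stands. The intended contrast can be inferred, the harm is a possible later misstatement rather than one already made, and the planned tests are usable. But the endpoint itself still speaks of patients with sepsis, not of patients who die, and a disclosure in a laboratory section does not narrow it.

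Two stronger readings are tempting and are not supported.

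- *That the endpoint simply duplicates the primary one.* This depends on which assay the primary endpoint means, and the documents do not settle it. The title separates serum from gene expression, and the secondary clause specifies the molecular level, so serum as primary and mRNA as secondary is a natural reading. Against that, the blood-sampling section applies the word *levels* to the PCR measures, and so does the secondary clause. The blood-sampling sentence is a weak guide, since it also assigns four cytokines to PCR while Table 1 lists primers only for GAPDH and PNX-14. Double counting is a risk to close, not an established fault.
- *That the other planned analyses fail for want of a non-septic group.* Relations of PNX-14 to mortality, severity and inflammatory markers are questions within sepsis and need no such group.

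**Conclusion.** The point holds for this one secondary clause. As worded, it asks about an effect of sepsis that the study cannot estimate, in size or in direction, from mRNA or from serum. This rests on exact algebra and on four stated design facts: only septic patients, one sample each, no non-septic reference, and calibration to survivors. The cancellation does not depend on whether the survivors' mean or median was the calibrator; only the geometric mean of exactly 1 does.

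No size of numerical error can be attached, and none is claimed. A reader might infer that the mortality results are undermined or that the clause should be dropped. Neither follows: the primary analyses do not use a non-septic reference, and removing a declared endpoint after results are known would be less transparent than narrowing it.

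**What to change.** 1. Keep the endpoint and reword it: *to compare PNX-14 mRNA expression at ICU admission between in-hospital deaths and survivors (RQ relative to survivors), and to evaluate the potential of PNX-14 levels as a translational biomarker.*
2. Add: *No conclusion is drawn about PNX-14 (mRNA or serum) in sepsis against a non-septic state.*
3. State whether PNX-14 levels in the primary endpoint means serum, mRNA or both, and report the RQ comparison so that it is not counted as both a primary and a secondary result.
4. Date the change and label it a clarification made after results were available. The label is needed because the Statistical Analysis section already reports Shapiro–Wilk p-values (0.12 and 0.17), a Levene p-value (0.018) and the inverse direction of the association with mortality.

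Cost: a few sentences, a narrower claim and a visible post-results label. Data, tests and primary analyses do not change.
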